Clinical Trial Protocol

NCT Number: NCT07043829

Protocol ID: PCSAEPF29-2021

Official Title: Effect of Consuming a Cimarrón Bean Extrudate Solution on Platelet Function and Postprandial Biochemical Parameters.

Sponsor: University of Talca, Chile.

Principal Investigator: PhD. [name]

Ethics Approval: Folio 29-2021 (Approved)

Version Date: June 19th, 2025

1. Background

The common bean (*Phaseolus vulgaris*), a legume with high nutritional value, has been shown to have beneficial effects on cardiovascular health. Its bioactive components, including proteins, polyphenols, and fiber, contribute to the modulation of platelet activity. Evidence from previous studies indicates that regular bean consumption may reduce inflammatory markers, oxidative stress, and overall cardiovascular risk, positioning it as a key functional food for the prevention and management of chronic diseases. Incorporating beans into the regular diet could represent a practical strategy to improve cardiovascular health and promote healthy eating habits in the general population. The primary objective of this trial is to obtain preliminary evidence on the acute capacity of the extrudate to reduce thrombotic activity under controlled conditions, minimizing potential confounding factors that could happen when using a delivery vehicle.

2. Objectives

General Objective

To analyze the acute effect of consuming a *Phaseolus vulgaris* L. var. Cimarrón extrudate solution on platelet function, postprandial blood glucose, and total plasma polyphenol levels.

Specific Objectives

1. To evaluate the effect of consuming SPVCE (Solution *Phaseolus vulgaris* L var. Cimarrón extrudate) on platelet function, assessed by PFA and platelet reactivity.
2. To determine the change in postprandial blood glucose after consuming SPVCE.

3. To quantify the effect of consuming SPVCE in postprandial total plasma polyphenol levels.

3. Study Design

Model Description: A single-arm, open-label, acute, non-randomized interventional study in which all participants consumed a single dose of a functional solution containing 10 grams of *Phaseolus vulgaris* L var. Cimarrón extrudate dissolved in water. No placebo or comparator group is included. Outcomes are measured before and after the intervention within the same participants to assess acute changes in platelet function, postprandial glycemia, and total plasma polyphenol levels.

4. Participants

Recruitment: Participants were recruited through posters, flyers, and announcements distributed in various university facilities, inviting the community to participate. Individuals expressing interest received a supplementary information sheet about the study and completed an initial digital survey for preliminary data collection. After reviewing the information, any questions regarding the study procedures were addressed. Written informed consent was obtained from each participant, and a copy was provided for their records.

Inclusion Criteria

1. Adults 20-59 years old, male or female.
2. Not taking medications affecting platelet function.
3. Voluntary participant, willingness to participate, and provide written informed consent

Exclusion Criteria:

1. Documented food allergies, especially to legumes or beans
2. Diagnosed with liver, kidney, autoimmune diseases, or severe illnesses such as cancer.
3. Diagnosed gastrointestinal diseases, including inflammatory bowel disease (e.g., Crohn's disease, ulcerative colitis), celiac disease, or any condition causing chronic gastrointestinal symptoms such as malabsorption, persistent diarrhea, or gastrointestinal bleeding

4. Use medication known to alter platelet function like antiplatelet agents (aspirin, clopidogrel); non-steroidal anti-inflammatory drugs (NSAIDs, ibuprofen, naproxen); Anticoagulants (Warfarin, heparin, direct oral anticoagulants like rivaroxaban or apixaban); Selective serotonin reuptake inhibitors (SSRIs) and other drugs known to impact platelet aggregation or hemostasis

5. Intervention

Phaseolus vulgaris L. var. *Cimarrón* Extrudate composition

Phaseolus vulgaris L. var. *Cimarrón* was processed using a hammer mill extruder equipped with a 6 mm screen, operating at an extrusion temperature of 120 °C, with a product exit temperature of 110 °C. Moisture content of the extruded flour was determined with a TK100 moisture sensor and measured at 9.5%. Processing was conducted at the University of Concepción, Chile. The proximate physicochemical characterization and an organoleptic evaluation performed by ANALAB S.A. (Santiago, Chile), indicated a beige to light brown coloration, an aroma reminiscent of nuts with a toasted note, a mild flavor with slight natural sweetness, and a fine, uniform, floury texture, smooth to the touch. The nutritional profile of the extruded flour is summarized in Table 1 (proximate and physicochemical analysis) and Table 2 (nutrition facts).

Table 1. Nutritional analysis carried out on *Phaseolus vulgaris* L. var. “Cimarrón”

Bioactive Compound	
Total Protein (g/100 g DM-Dumas)	29.1
Soluble Protein (mg/mL)	3.8
Amino acids (mg/g Protein)	
Gly.His	55.3
Thr	34.3
Val	36.9
Met	7.4
Ile	31.5
Leu	58.4
Phe	45.3
Lys	54.4
EAA s	323.4
Asp	78.1
Glu	115.0
Ser	48.1

Arg	58.7
Ala	34.4
Pro	34.0
Tyr	24.8
NEAAs	394.3
Macro elements (g/10 g DM)	
P	4.6
K	15.8
Ca	1.1
Mg	1.9
Micro elements (mg/10g DM)	
Mn	14.0
Zn	45.3
Cu	10.3
Fe	105.0
B	18.0
Sugar	
RFO (mmol/100g DM)	5.0
Sucrose (g/ 100g DM)	2.3
Antioxidant capacity	
TPC (mg GA/ 100g DM)	74.5
ORAC (umol TE /100g DM)	9474.9

Table 2. Nutrition facts- *Phaseolus vulgaris* L. var. Cimarrón Extrudate

Nutrition Facts	100 g	Portion (10 g)
Calories (kcal)	227.9	22.79
Total Fat (g)	0.4	0.04
Sodium (mg)	0.62	0.062
Total Carbohydrate (g)	44.29	4.29
Dietary Fiber (g)	17.83	1.78
Total Sugars (g)	6.82	0.68
Includes 0g Added Sugars	0	0
Protein (g)	29.1	2.5

Time line

Participants were scheduled in advance and instructed to arrive after an overnight fast of 10–12 hours. Upon arrival, they completed a digital basic health assessment questionnaire covering medical history, current health status, dietary and nutritional habits, tobacco and alcohol consumption, education level, and socioeconomic status. A phlebotomist inserted an intravenous line to maintain venous access for blood collection, and participants remained at rest throughout the intervention.

1. At time 0 (baseline), blood samples were collected in two tubes containing 3.2% sodium citrate (Ez MedLab Co., Zhejiang, China) for baseline platelet function analysis (platelet reactivity and PFA) and quantification of total plasma polyphenols, and in one serum separator tube (Ez MedLab Co., Zhejiang, China) for baseline glucose measurement.
2. Two hours after SPVCE consumption, an additional serum separator tube was collected for postprandial glucose measurement and quantification of total plasma polyphenols.
3. Six hours after SPVCE consumption, blood samples were again collected in two sodium citrate tubes for postprandial platelet function analysis (platelet reactivity and PFA) and quantification of total plasma polyphenols.

Preparation and administration details

1. **Fasting state:** about 10 to 12 hours of nocturnal fasting; the participant can drink water while in the fasting state.
2. **Administration of SPVCE:** The participant has 10 to 15 minutes to drink the SPVCE. The research team made the SPVCE, and the self-team supervised the administration.

7. Outcomes

Primary endpoint

- **Platelet function measured by flow cytometry assay:** binding fluorescein isothiocyanate–conjugated anti-fibrinogen antibody (FITC) and PE-conjugated anti-P-selectin (PE) antibody after stimulation with ADP (0.03–30 μ M), collagen-related peptide (CRP; 0.003–3 μ g/mL), and thrombin receptor activator peptide 6 (TRAP-6; 0.05–15 μ M). Measurements performed using a FACSLytic flow

cytometer (BD, San Diego, USA). Analysis performed by Thrombosis Center Research, Talca, Chile.

Secondary endpoints

- 1. Platelet Function (Closure Time):** Measured by PFA-200 (Collagen+ADP cartridge, Siemens Healthcare, Marburg, Germany) at 0 h and 6 h on whole blood. Analysis performed by Thrombosis Center Research, Talca, Chile.
- 2. Baseline and postprandial Glucose:** Serum glucose measured by GOD-POD (glucose oxidase-peroxidase) enzymatic colorimetric method using BS300 Mindray (Shenzhen, China) at time 0h (baseline) and 2 h postprandial. Analysis performed by Clinic laboratory Talca, Chile.
- 3. Plasma total polyphenols concentration:** Prussian blue colorimetric method, measured in plasma at 0 h, 2 h, and 6 h. Analysis performed by Thrombosis Center Research, Talca, Chile.

Safety endpoints: Adverse events, vital signs, and routine clinical laboratory safety tests. Any clinically relevant abnormality will be recorded and reported per the ethics committee's requirements.

Sample handling: specify tubes and processing:

- 1. Flow cytometry platelet reactivity:** Whole blood anticoagulated with 3.2% sodium citrate processed according to Thrombosis Center SOPs, centrifuged at 1200 rpm for 12 minutes at T° ambient, obtaining platelet-rich plasma (PRP). Agonist time-to-stimulation: 10 minutes at ambient temperature and staining 20 minutes at ambient temperature
- 2. PFA-200:** Whole blood anticoagulated with 3.2% sodium citrate processed to Thrombosis Center SOPs in recommended cartridge tube tested within manufacturer's timeframe: 30 minutes after sampling at 15-25 °C.
- 3. Glucose:** Serum separator tubes, centrifuge at 3000 rpm for 8 minutes at ambient temperature, and analyze per Clinic Lab. Talca SOP.
- 4. Total polyphenols:** Whole blood anticoagulated with 3.2% sodium citrate processed to Thrombosis Center SOPs, centrifuged at 3000 rpm for 8 minutes at ambient temperature, obtaining platelet-poor plasma (PPP), aliquot and store at -80°C until assay if not run immediately.

Laboratories: Thrombosis Center Research, University of Talca (Platelet function assays and total polyphenols), and Clinic Laboratory Talca (glucose).

Visit schedule & sample timing

- 1. Day 0 (Treatment):** Participants arrived in fasting conditions (≥ 8 hours).
- 2. Baseline samples at T0h:** PFA-200, flow cytometry (reactivity), serum glucose, plasma total polyphenols. Administer 10 g extrudate in 500 ml water (supervised).
- 3. Post-dose samples:** T2h-serum glucose, plasma total polyphenols; T6h-PFA-200 Flow cytometry, plasma total polyphenols. Record AEs and vital signs throughout.

Discharge/follow-up: The participant has signed a request for sample storage and subsequent use of the samples in future research. Depending on the option selected (Acceptance or Rejection), the samples will be stored accordingly, labeled with the corresponding code, or discarded following the biological sample disposal protocol of the University of Talca, Chile.

8. Sample size and Statistical considerations

Planned enrollment: 30 participants

Statistical software: GraphPad Prism 10.1.1.

Statistical Plan: Paired analysis comparing pre- and post-dose measures, two-sided $p < 0.05$. More details in the SAP appendix.

9. Criteria for Withholding and Stopping

Withholding Criteria (no intervention on study day):

The investigational product will **not be administered**, and the participant's study visit will be suspended for the remainder of that scheduled 8-hour session if any of the following are present at baseline (pre-dose) or detected during the immediate pre-administration checks:

1. Acute illness or fever on the study day.
2. Fasting blood glucose ≥ 126 mg/dL or ≤ 60 mg/dL at baseline measurement.
3. Blood pressure $\geq 160/100$ mmHg at baseline assessment.

4. Self-reported moderate/severe gastrointestinal symptoms within 24 hours before the visit (e.g., vomiting, severe diarrhea, uncontrolled nausea).
5. Any acute condition deemed by the investigator to increase participant risk or compromise data integrity.

Action: If withholding criteria are met, the product will **not** be given during that 8-hour session. The study physician documents the reason, provides appropriate care/advice, and notifies the principal investigator. Rescheduling of the visit may occur only according to the trial's rescheduling policy (if allowed by the protocol); otherwise, the visit is recorded as not completed.

Stopping Criteria (Immediate cessation during session):

The study intervention will be **stopped immediately** for an individual participant during the 8-hour session if any of the following occur:

1. Any **serious adverse event (SAE)** possibly, probably, or related to the product (e.g., anaphylaxis, respiratory distress, hospitalization).
2. Acute clinically significant change in monitored clinical parameters judged to be related to the product (for example: new onset chest pain, severe hypotension or hypertension not responsive to initial measures, severe arrhythmia).
3. New laboratory or point-of-care result during the visit indicating acute organ injury (e.g., markedly abnormal glucose) that the investigator deems unsafe to continue.
4. Severe or worsening gastrointestinal reaction during the session (e.g., persistent vomiting, dehydration) that requires medical intervention.
5. Participant requests to stop or withdraw consent at any time.

Action: On stopping, immediate medical evaluation is provided, the event is documented in the case report form, the principal investigator is notified, and appropriate medical referral (including emergency care) is arranged if needed. The participant's further participation in subsequent visits will be decided according to the protocol and safety assessment.

Additional operational details

1. Who decides: the study physician and/or principal investigator make withholding/stopping decisions. Site staff follow their instructions.

2. Monitoring during the 8-hour visit: vital signs and symptom checks per protocol schedule; any trigger must be recorded with time and action taken.
3. Reporting: all SAEs and stopping events are reported per the trial safety reporting plan and institutional requirements.
4. Re-enrollment/rescheduling: any decision to allow the participant to return for another 8-hour session must follow the protocol's eligibility and rescheduling rules and occur only after medical clearance.

10. Data management and Ethics

Records will be kept confidential by the responsible researcher. Participant names or identifiers will not be used. Blood samples will be labeled with codes and will not be linked to personal data. Identity and health information will not be disclosed and will remain confidential. Study approved by the University of Talca Scientific Ethic Committee (Folio 29-2021).

Statistical Analysis Plan (SAP)

NCT Number: NCT07043829

Protocol ID: PCSAEPF29-2021

Official Title: Effect of Consuming a Cimarrón Bean Extrudate Solution on Platelet Function and Postprandial Biochemical Parameters.

Sponsor: University of Talca, Chile.

Principal Investigator: PhD. [name]

Ethics Approval: Folio 29-2021 (Approved)

Version Date: June 19th, 2025

1. Introduction: This Statistical Analysis Plan (SAP) outlines the methods and procedures for analyzing the data from the clinical trial investigating the acute effects of a Cimarrón Bean Extrudate solution on platelet function and postprandial biochemical parameters.

2. Analysis Populations

- **Per-protocol (pp) population:** Includes all participants who complete the 8-hour observation period and have valid measurements for the outcomes of interest without major protocol deviations (e.g., incomplete fasting, incomplete product ingestion, prohibited medication use). Sensitivity analyses will be conducted in the PP population to verify robustness.
- **Available Case Analysis:** An analysis based on all available data pairs for each outcome; participants with missing paired data will be excluded from that specific analysis.

3. Software: All statistical analyses will be performed using *GraphPad Prism version 10*.

4. General Analysis Design

- The planned sample size is **n = 30**.
- Measurements were obtained at baseline (0 h, pre-ingestion) and at **2 h** and **6 h** after consumption of the extrudate solution.

- Continuous variables will be expressed as mean \pm standard deviation (SD) when approximately normally distributed, or median [interquartile range, IQR] when non-normal.
- Categorical variables will be presented as frequency and percentage. For each time point, the mean/median and change from baseline will be reported.

5. Assessment of Normality and Homogeneity

Normality of data will be evaluated using the Shapiro–Wilk test, and homogeneity of variances will be assessed using Levene’s test where applicable. All statistical tests will be two-sided with the significance level set at $p < 0.05$.

6. Primary Endpoint

- Platelet Function (Flow Cytometry – Dose–Response Analysis): For each activation marker (P-selectin and fibrinogen) and agonist (ADP, TRAP-6, CRP), dose–response curves will be generated using non-linear regression to determine EC₅₀, maximum response, minimum response, and response span per participant. Comparisons of these curve-derived parameters between baseline (0 h) and 6 h post-ingestion will be performed.

The analysis will proceed as follows: For curve-derived parameters (EC₅₀, maximum, minimum, and response span), normality of paired differences between baseline and 6 h will be assessed using the Shapiro–Wilk test. If data are normally distributed, paired t-tests will be used for comparisons; if non-normal, Wilcoxon signed-rank tests will be applied. For the dose–response curves themselves, a two-way ANOVA will be performed to evaluate the effects of treatment (baseline vs. 6 h) and agonist concentration. If assumptions for parametric analysis are met, Sidak’s multiple comparisons post hoc test will be applied. If assumptions are not met and the analysis is non-parametric, a corresponding non-parametric alternative to two-way ANOVA will be used, followed by Dunn’s multiple comparisons post hoc test. Data will be presented as mean \pm SD for normally distributed data and median [IQR] for non-normal data

7. Secondary Endpoints

1. **Platelet Function (Closure Time – PFA-200):** Paired differences between baseline (0 h) and 6 h will be analyzed after testing for normality with the

Shapiro–Wilk test. Normally distributed data will be compared using a paired t-test, and non-normal data using the Wilcoxon signed-rank test.

2. **Baseline and Postprandial Glucose:** Differences between 0 h and 2 h will be analyzed using the same normality testing and paired statistical approach (t-test or Wilcoxon).
3. **Plasma Total Polyphenols Concentration:** Repeated measures at 0 h, 2 h, and 6 h will be analyzed using one-way repeated measures ANOVA if normality assumptions are met, followed by an appropriate post hoc test (e.g., Tukey's or Sidak's) for parametric data. If non-parametric, the Friedman test will be used, followed by Dunn's multiple comparisons post hoc.

8. Missing Data Handling

- The primary analysis will be conducted as an available-case analysis: only complete pairs of baseline and post-dose measurements will be included for paired comparisons, excluding any missing pairs. The number of pairs included will be reported for each analysis.
- If missing data in the primary variable is $\leq 5\%$, only available-case analysis will be performed without imputation.
- If missing data exceeds 5% or is suspected not to be missing completely at random, sensitivity analyses will be conducted using appropriate methods such as:
 - Linear mixed models for repeated measures (assuming Missing At Random), or
 - Multiple imputation (e.g., predictive mean matching) and comparison with available-case results.
- Participants lacking estimable parameters for a specific variable will be excluded from analyses involving that parameter; actual sample sizes will be reported accordingly.

9. Multiple Comparisons Correction

No formal correction for multiple comparisons will be applied. The primary endpoint analyses are limited to a small set of predefined parameters (EC_{50} , max, min, span) for key activation markers and agonists. Secondary endpoint analyses will be considered exploratory. Given the focused nature of the primary analyses and the sample size, results will be interpreted with caution regarding multiplicity. Where applicable, post hoc tests controlling type I error (e.g., Sidak's or Dunn's tests) will be used following ANOVA or non-parametric analyses.

10. Safety and Adverse Events

Gastrointestinal symptoms and any adverse events will be summarized as frequencies and percentages. Where applicable, events will be reported by post-ingestion time point.

11. Sample Size and Power

The planned sample size of **n = 30** is based on feasibility and prior experience in acute postprandial studies. With n = 30 for paired comparisons, the study has approximately **80% power** to detect a medium effect size (Cohen's $d \approx 0.5$) at $\alpha = 0.05$ (paired t-test).

12. Presentation of Results

Results will be presented in tables and figures. Tables will include descriptive statistics per time point, changes from baseline with 95% confidence intervals, and adjusted p-values where applicable. Figures will present time–response profiles, dose–response curves, and bar plots of key comparisons.

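### The protocol contradicts itself on the 2 h polyphenol sample (serum tube or citrate plasma); if it was serum, tube type is confounded with the 2 h time point

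*Combined protocol and SAP*

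**What the plan says.** The Time line in protocol section 5 is the only place that states which tubes were drawn at each time.

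- At 0 h, "blood samples were collected in two tubes containing 3.2% sodium citrate" for platelet function and polyphenols. A separate serum separator tube was for glucose only.
- At 2 h: "Two hours after SPVCE consumption, an additional serum separator tube was collected for postprandial glucose measurement and quantification of total plasma polyphenols". No other tube is listed.
- At 6 h, "blood samples were again collected in two sodium citrate tubes", again for platelet function and polyphenols.

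Three statements elsewhere in the protocol point the other way.

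- Section 7, secondary endpoint 3: "Prussian blue colorimetric method, measured in plasma at 0 h, 2 h, and 6 h".
- Section 7, Sample handling, item 4 (total polyphenols): "Whole blood anticoagulated with 3.2% sodium citrate processed to Thrombosis Center SOPs, centrifuged at 3000 rpm for 8 minutes at ambient temperature". The product is platelet-poor plasma, and no exception is made for 2 h.
- Visit schedule and sample timing, item 3: at 2 h the matrix is serum for glucose and plasma for total polyphenols.

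SAP section 7, item 3 gives the analysis: "Repeated measures at 0 h, 2 h, and 6 h will be analyzed using one-way repeated measures ANOVA if normality assumptions are met". Post hoc tests follow, with Friedman and Dunn as the non-parametric route. There is no term, correction or sensitivity analysis for tube or matrix. Protocol section 3 states that there is no placebo or comparator group.

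**The concern.** A serum separator tube cannot yield citrate platelet-poor plasma, so at least one of these statements is wrong. If the wrong one is the Time line, the repair is editorial. If the Time line is right, the 2 h value comes from a different matrix than the values on either side of it.

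In that case every participant has citrate plasma at 0 h, serum at 2 h and citrate plasma at 6 h. Matrix and time then coincide exactly, and with a single arm no model fitted to the planned data can tell a tube effect from a product effect. Two of the three pairwise contrasts involve 2 h. A constant matrix offset would appear as a rise and fall, or as a dip and recovery, without any change in the participants. Polyphenols are the subject of specific objective 3 and part of the general objective.

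**Working it through.** The plan states no figure for this point, so there is none to reproduce. The check has three steps: compare the text, size the possible offset, and find how often the planned kind of test would react to it.

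**Step 1. The text side by side, polyphenols only**

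| Source (protocol) | 0 h | 2 h | 6 h |
|---|---|---|---|
| Section 5, Time line | citrate | serum separator | citrate |
| Section 7, secondary endpoint 3 | plasma | plasma | plasma |
| Section 7, Sample handling, item 4 | citrate plasma | citrate plasma (no exception made) | citrate plasma |
| Visit schedule | plasma | plasma | plasma |

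The conflict is confined to the 2 h column. No section lists a citrate tube at 2 h.

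**Step 2. Possible offset from dilution alone**

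Assumptions not in the documents: nine parts blood to one part liquid citrate, and haematocrit H from 0.36 to 0.50.

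Ratio of serum to citrate plasma = [0.9(1 − H) + 0.1] / [0.9(1 − H)].

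- H = 0.36: 0.676 / 0.576 = 1.174, so serum reads 17% higher.
- H = 0.45: 0.595 / 0.495 = 1.202, or 20% higher.
- H = 0.50: 0.550 / 0.450 = 1.222, or 22% higher.

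This covers dilution only. The documents give no serum-to-plasma difference for the Prussian blue assay, and they do not show whether the laboratory's procedures correct for dilution.

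**Step 3. How often a false 2 h change would be declared**

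Inputs from the documents: n = 30, two-sided 0.05, three time points. Assumed: no true change, an offset of +20%, and an SD of paired differences of 20%, 30% or 40% of the mean (no SD for this assay is given).

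Sidak level for three comparisons = 1 − 0.95^(1/3) = 0.01695, so the critical t on 29 degrees of freedom is 2.534. Noncentrality = (offset / SD) × √30.

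| SD of paired differences | Noncentrality | False 2 h versus 0 h result, Sidak level |
|---|---|---|
| 20% | 5.48 | 99.7% |
| 30% | 3.65 | 86% |
| 40% | 2.74 | 59% |

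Without adjustment, the 30% row would be 94%. The Sidak figure is closer to the SAP, which names Tukey or Sidak as its parametric post hoc tests.

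Smaller offsets at the Sidak level: +17% with SD 30% gives 71%. An offset of +10% gives 59% with SD 20% and 26% with SD 30%.

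A simulation of the repeated-measures ANOVA itself agrees (10,000 trials per setting, no true change, assumed between-subject CV 20%, within-subject CV 10%, 15%, 20% and 30% in turn):

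- Offset +20%: the ANOVA rejects in 100%, 99.8%, 95% and 66% of trials.
- Offset +10%: 97%, 70%, 45% and 22%.
- Offset −10%: 99%, 78%, 51% and 25%, now as a false dip.
- Same matrix throughout: about 5%, as intended. A false 2 h rise then appears in about 1%.

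The 0 h versus 6 h contrast, tested on its own paired differences, stays at about 1.5% to 2% in every setting, which is its Sidak level.

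**The case against.** The strongest reply is that the Time line sentence may simply omit a tube. The visit schedule separates the two matrices at 2 h, the endpoint definition says plasma at all three times, the handling text makes no exception, and the Time line sentence itself speaks of plasma polyphenols. On that view nothing was mismeasured. This stands as far as it goes: the documents do not establish that serum was assayed. It does not remove the contradiction. The Time line gives the serum tube one purpose at 0 h and two at 2 h, which makes a slip less likely. Platelet function is not measured at 2 h, so a citrate tube would have been needed for polyphenols alone, and none is listed.

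A reader might also infer that the bias must run upward, in the hoped-for direction. The documents do not support that. Dilution points upward, but the net offset for this assay is unknown and could be smaller, could run downward, or could hide a real rise.

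A reader might further infer that objective 3 could be declared met on an artefact. The objective is only to quantify an effect, with no success criterion, and SAP section 9 treats secondary analyses as exploratory. That limits the consequence, but it does not make values from two matrices comparable.

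**Conclusion.** The contradiction is certain and has to be resolved. The bias is conditional: it arises only if the 2 h polyphenol value came from the serum tube. It would then be inseparable from the 2 h time point under SAP section 7, item 3, by either the ANOVA or the Friedman route.

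Its size rests on assumptions. Under the assumed fill and haematocrit, dilution alone gives about 17% to 22%. At a +20% offset, the false-positive rate for 2 h versus 0 h runs from about 59% to over 99% across the assumed SDs, and it falls quickly if the net offset is smaller. Near-certainty of a false peak is therefore not supported.

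The reach is narrow: one secondary endpoint, at one time point. The 0 h versus 6 h polyphenol comparison, flow cytometry, closure time and glucose are not affected.

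**What to change.** Begin with the facts, because the protocol describes sampling in the past tense. Confirm from laboratory records which tube supplied the 2 h polyphenol measurement. Then make the Time line, secondary endpoint 3, Sample handling item 4 and the visit schedule agree.

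- **Citrate was used:** correct Time line item 2. The analysis does not change, and the cost is one sentence.
- **Sampling is still under way:** collect a 3.2% citrate tube at 2 h from the venous line already in place, and list it in the Time line. The cost is one small tube per participant with no new puncture. Participants already sampled in serum only are handled as below.
- **Only serum exists at 2 h:** amend SAP section 7, item 3 so that the inferential polyphenol comparison is 0 h versus 6 h in citrate plasma, tested as a paired difference. Report 2 h descriptively with its matrix stated. The cost is the loss of the 2 h contrast. Keeping that contrast would need a documented serum-to-plasma bridging correction for this assay, and the documents contain none.

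In every case the report should state the matrix at each time point.

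### Neither the protocol nor the SAP provides for hiding the time point (0 h or 6 h) from those who gate, fit and accept the primary flow-cytometry data

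*Combined protocol and SAP*

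**What the plan says.** - **Design.** Protocol section 3 describes "A single-arm, open-label, acute, non-randomized interventional study" and adds: "No placebo or comparator group is included". The change within each participant is therefore the whole treatment contrast.
- **Primary assay.** Protocol section 7 defines the endpoint as antibody binding for fibrinogen and P-selectin after stimulation with ADP, CRP and TRAP-6 ("Measurements performed using a FACSLytic flow" cytometer). It assigns the analysis to the Thrombosis Center. The list of laboratories in the same section reads "Laboratories: Thrombosis Center Research, University of Talca (Platelet function assays and total polyphenols", and the protocol opens with "Sponsor: University of Talca, Chile".
- **Primary analysis.** SAP section 6 uses non-linear regression to obtain EC50, "maximum response, minimum response, and response span per participant", and compares each parameter between 0 h and 6 h. It gives no curve model, constraints or rule for accepting a fit.
- **Exclusions.** SAP section 8 drops a participant from the analysis of any parameter that is not estimable. It does not say what makes a parameter estimable.
- **Coding.** Protocol section 10, in a paragraph on confidentiality, states: "Blood samples will be labeled with codes and will not be linked to personal data". It does not say whether the code shows or hides the time point.
- **Masking.** Neither document mentions masking of the cytometry analyst, the curve fitter or the statistician.

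**The concern.** Turning cytometry events into a marker value takes a platelet gate and, if the readout is percent positive, a positivity threshold. Turning those values into EC50, maximum, minimum and span takes a curve model, constraints and a decision on whether the fit is acceptable. The documents fix none of these beyond naming non-linear regression and the four parameters, so judgement remains at each step.

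If that judgement is exercised with the time point in view, expectation can influence it. The Background section gives the expectation a direction, since the trial looks for preliminary evidence that the extrudate lowers thrombotic activity. In a randomised comparison a reader's habits tend to fall equally on both arms. Here they would fall on the contrast itself.

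The primary endpoint also yields 2 markers × 3 agonists × 4 parameters = 24 comparisons, and SAP section 9 applies no formal correction. A single gating habit could move several of them together.

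**Working it through.** **Inputs.** From the documents: 30 pairs (Protocol section 8, SAP section 4); two-sided 0.05 (SAP section 5); paired t-test, d = 0.5, power of about 80% (SAP section 11). The reading shift b is assumed, because the documents give no figure for it.

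**1. Reproduce the plan's power.** By the normal approximation, power = Φ(d√n − 1.96) = Φ(0.5 × 5.477 − 1.96) = Φ(0.779) = 78.2%, which agrees with the stated figure of about 80%. The exact paired t-test (non-central t, 29 df, non-centrality 2.739) gives 75.4%. Masking changes neither figure.

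**2. Smallest change that reaches significance.** The critical t on 29 df is 2.045, so an observed mean change of 2.045/√30 = 0.373 SD of the paired difference gives p < 0.05.

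**3. Effect of a systematic reading shift.** Set the true effect to zero and let handling of the files add b SD to every paired difference. The chance of p < 0.05 is the exact two-sided t-test power at non-centrality b√30.

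| Assumed shift b (SD) | b√30 | Chance of p < 0.05, one parameter |
|---|---|---|
| 0 | 0 | 5.0% |
| 0.10 | 0.548 | 8.3% |
| 0.20 | 1.095 | 18.5% |
| 0.30 | 1.643 | 35.5% |

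**4. Which parameters would move.** This depends on the curve. A constant offset at every concentration changes minimum and maximum but cancels in span and leaves EC50 alone. Proportional scaling also leaves EC50 alone.

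A threshold change behaves differently. Suppose percent positive is the readout, fluorescence is normal with equal spread, and the threshold moves from the 99th to the 97.5th percentile of unstimulated platelets (2.33 to 1.96 SD, a move of 0.37 SD) at one time point only:

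- the minimum goes from 1.0% to 2.5%;
- a point at 50% goes to Φ(0.37) = 64%;
- with a maximum of 95%, the maximum becomes about 97.8% and span goes from 94.0 to about 95.3 points;
- with a maximum of 70%, span rises by about 10 points.

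The documents contain no curves and do not name the readout, so this shows a mechanism only.

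**The case against.** The strongest reply is that silence is not evidence. A reader might infer that the analysts know the time point, or that gates are set separately at 0 h and 6 h. The documents say neither. The codes may already conceal the time point, and the laboratory SOPs, cited in Protocol section 7 for sample processing, are not reproduced. Gating is not mentioned at all, so operator dependence is inferred from the type of assay and from the unspecified fit rules. This stands, and it limits the point to what the plan fails to provide for.

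A reader might also treat use of the sponsor university's own laboratory as a fault. It is not one, and masking would not change it. Nor is the plan one-sided: the general objective is worded neutrally and the tests are two-sided.

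Next, the exclusion rule removes a whole pair, not one time point. That is correct. However, someone who sees both curves and knows which is which could still be influenced over which pairs to drop.

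Finally, this is a preliminary, uncontrolled study, and masking the readers leaves time of day, prolonged fasting and rest, and the indwelling line confounded with the 6 h measurement. That also stands. It limits the benefit of masking, but reader expectation is the one source of bias here that can be removed without new data.

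**Conclusion.** The point holds as a gap in the plan. Nothing in either document protects the offline reading of the primary endpoint from knowledge of the time point, and the design has no control arm to absorb a systematic difference in reading. It should be closed before analysis.

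The documents give neither the size nor the direction of any bias. The range of about 8% to 36% rests wholly on an assumed shift of 0.10 to 0.30 SD, applied consistently to one parameter, with 30 complete pairs, a paired t-test and no true effect. It should not be read as an estimate for this trial. The threshold example in the working, where the minimum more than doubles, is likewise hypothetical and does not support a claim that all four parameters would be distorted.

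**What to change.** Add the following to Protocol section 7 and SAP sections 6 and 8:

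1. Before analysis, an existing team member who does no gating or fitting recodes the raw cytometry files. Each participant's two sets share a neutral pair code and are labelled A and B in random order. File names and any acquisition time stored in the file are concealed.
2. One gate and threshold is set per pair, from whatever control or lowest-stimulation tubes were run, and applied unchanged to A and B. The shared pair code makes this possible while the time point stays hidden.
3. The curve model, constraints and a definition of estimable are written down in advance and applied identically to A and B.
4. All gates, fits and exclusions are locked before the A/B key is released.

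Fresh samples drawn 6 h apart cannot readily be masked at acquisition, so the masking applies to the offline work. If the codes already hide the time point, one sentence saying so settles item 1; items 2 to 4 are still needed.

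The cost is recoding by existing staff and a modest delay, with no new samples or assays. Much of the protocol is written in the past tense, so sampling may be finished; the fix still works provided the raw files were kept, which the documents do not state.
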